- To develop a specimen bank comprising liver tissue, serum, plasma, and DNA obtained from NAFLD or cryptogenic cirrhosis patients
- To provide a resource for clinical trials and ancillary studies of the pathogenesis, natural history, and treatment of NAFLD or cryptogenic cirrhosis

Type of study

- Observational

Population

- Patients at least age 2 years with definite or suspected NAFLD or cryptogenic cirrhosis

Inclusion criteria

- Histologic diagnosis of NAFLD or histologic diagnosis of cryptogenic cirrhosis or suspected NAFLD on the basis of imaging studies suggestive of NAFLD or clinical evidence of cryptogenic cirrhosis
- Absence of regular or excessive use of alcohol within 2 years prior to initial screening
- At least age 2 years at time of initial screening
- Consent

Exclusion criteria

- Clinical or histologic evidence of alcoholic liver disease
- Evidence of other chronic liver disease
- History of total parenteral nutrition, biliopancreatic diversion, or bariatric surgery
- Short bowel syndrome
- Suspected or confirmed hepatocellular carcinoma
- Known HIV positive
- Other condition that is likely to interfere with study followup

Recruitment

- To sample size goal
- 36 month period

Duration of followup

- 48-192 weeks

NAFLD Database Protocol

Design synopsis

Outcome measures

- Liver histology scores (derived from historical liver biopsy at entry, standard of care biopsy done during screening or followup, or liver biopsy done for NASH CRN trials)
- ALT, AST levels
- Lipid profile
- Imaging studies of NAFLD
- Glucose, insulin levels
- Body mass index
- Health related quality of life
- Alcohol consumption
- Nutritional intake
- Physical activity
- Medication for NAFLD

Visit schedule

- Screening/entry into NAFLD Database: enrollment must occur within 120 days of initiation of screening
- Followup visits at 24 weeks, 48 weeks, 96 weeks, 144 weeks, and 192 weeks

Sample size

- Total of 1500 patients (~200/clinic)
-

NAFLD Database Protocol

1. Background and rationale

1.1. Historical background and goals

Nonalcoholic fatty liver disease (NAFLD) is a spectrum of liver conditions associated with fat accumulation that ranges from benign, non-progressive liver fat accumulation to severe liver injury, cirrhosis, and liver failure. NAFLD appears to be highly prevalent within the United States. The spectrum of NAFLD encompasses simple nonalcoholic steatosis (nonalcoholic fatty liver [NAFL] and nonalcoholic steatohepatitis (NASH) in which there is ballooning degeneration (with or without Mallory bodies) and/or fibrosis. In severe cases, NASH may progress to cirrhosis, in which steatosis may be present or absent. In the latter circumstance, end-stage NASH may evolve into and contribute to one category of cryptogenic cirrhosis. The pathology of NASH closely resembles alcoholic liver disease but occurs in patients who drink little or no alcohol. NASH is most common in adults above the age of 40 who are overweight or have diabetes, insulin resistance or hyperlipidemia. However, the disease also occurs in children and in persons who are not obese or diabetic. Currently, there is no established effective therapy for NASH, and its natural history and prognosis are not well understood. In 2002, the National Institute of Diabetes and Digestive and Kidney Diseases (NIDDK), through the mechanism of RFA-DK-01-025, established a Clinical Research Network (CRN), the goal of which is to facilitate and perform clinical, scientific, epidemiological and therapeutic research in NASH.

1.2. Clinical Research Network (CRN)

The NASH Clinical Research Network (NASH CRN) is a cooperative network of eight clinical centers and one Data Coordinating Center (DCC). Clinical centers are responsible for proposing protocols, participating in their overall development, recruiting patients, conducting the research, and disseminating research findings. The individual clinical centers participate in a cooperative and interactive manner with one another and with the DCC in all aspects of the NASH CRN. The DCC supports protocol development; provides sample size calculations, statistical expertise, forms, and data analysis; supports manuscript preparation; and provides overall study coordination and quality assurance, including coordination of the activities of the Data and Safety Monitoring Board, the Steering Committee and other standing committees. The DCC also collaborates with the NIDDK Biosample (plasma, serum, and liver tissue) and Genetics (DNA) Repositories.

A Steering Committee composed of the principal investigators of each clinical center in the Network, the principal investigator of the DCC, and the NIDDK Project Scientist is the main governing body of the NASH CRN. The Steering Committee has primary responsibility for the general organization of the NASH CRN, finalizing common clinical protocols and facilitating the development of a standardized nomenclature, diagnostic criteria, histological definitions, and the necessary components to the common database on patients. The Steering Committee is responsible for the conduct and monitoring of studies and reporting study results.

NAFLD Database Protocol

2. Objectives and hypotheses of the NASH CRN

2.1. Primary objectives of the NASH CRN

- To elucidate, through the co-operative effort of a multidisciplinary and multicenter group of collaborators, the etiology, natural history, diagnosis, treatment, and prevention of NAFLD and in particular its more severe form of NASH and its complications
- To construct a database of a large cohort of patients with NAFLD (or a history of NAFLD) with a broad range of severity, recruited by the NASH CRN (NAFLD Database). Core data collection will include clinical, demographic, laboratory, imaging, and histological features
- To develop a specimen bank comprised of liver tissue, serum, plasma, and DNA obtained from recruited patients
- To undertake clinical trials of promising therapies for NAFLD or cryptogenic cirrhosis

2.2. Secondary objectives of the NASH CRN

- To provide a resource for developing clinical and pathological criteria for standardizing diagnostic and staging criteria for NAFLD or cryptogenic cirrhosis
- To provide a resource for developing clinical and pathological criteria and measures and endpoints for therapeutic studies of NAFLD or cryptogenic cirrhosis
- To provide a resource for ancillary studies of the pathogenesis, diagnosis, natural history and treatment of NAFLD or cryptogenic cirrhosis

2.3. Hypotheses to be tested using the NAFLD Database

The NAFLD Database will collect information that will enable critical hypotheses pertinent to the etiology, pathogenesis, and natural history of NAFLD to be tested. These include:

- The severity and rate of progression of NAFLD is related to alcohol consumption
 - The severity and rate of progression of NAFLD is related to body mass index
 - The severity and rate of progression of NAFLD is related to dietary calorie consumption
 - The severity and rate of progression of NAFLD is related to physical activity
 - The severity and rate of progression of NAFLD is related to the presence and severity of diabetes
 - The natural history of NAFLD includes progression to cirrhosis without histological features of NAFLD (cryptogenic cirrhosis)
 - The risk for the development of NAFLD and NASH in overweight/obese individuals is greater in Hispanic and Caucasian racial/ethnic groups than in African American or Asian groups
 - A family history of liver disease is more frequently associated with more advanced or more rapidly progressive NAFLD
-

NAFLD Database Protocol

3. Scientific background

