4.4. Target composition of Database population

Patients with primary NAFLD including selected patients with cryptogenic cirrhosis and patients with secondary NAFLD not directly associated with gastrointestinal surgery/bypass will be enrolled in the Database. Patients with acute syndromes of microvesicular fatty liver disease will not be enrolled. Total patient recruitment into the Database is estimated at approximately 1500 patients (about 200 patients per clinical center). Twenty percent of the patients are expected to have suspected NAFLD, 15% are expected to have cryptogenic cirrhosis, and 65% are expected to have definite NAFLD. Thirty to forty percent are expected to be diabetic (about 550 patients). At least 25% of patients are expected to be in the pediatric age group. Site specific enrollment of patients in the category of “suspected NAFLD” will be monitored by the DCC; there will be a cap on the total patients enrolled in this category set at 20% of the projected total enrollment. Of the patients with cryptogenic cirrhosis, the group enrolled with “suspected cryptogenic cirrhosis” will be similarly monitored to limit the total to 50% of all patients with cryptogenic cirrhosis.

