5.1. Inclusion criteria

In order to be enrolled in the Database, patients must satisfy all of the following:

- Alcohol use history consistent with NAFLD
- Imaging study suggestive of NAFLD or biopsy materials meeting histologic definition of NAFLD or cryptogenic cirrhosis (histology must be confirmed by local NASH CRN pathologist) or imaging study and clinical findings meeting the criteria for suspected (clinical) cryptogenic cirrhosis (see section 4.3)
- Ability and willingness of patient or legal guardian/representative to give written, informed consent
- Age at least 2 years at initial screening visit
- Ability and willingness to participate in followup

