6.7. Database contents**6.8. Serum, plasma, DNA, and liver tissue for banking**

Fasting serum, plasma, DNA, and stored liver tissue will be banked for NASH CRN substudies or ancillary studies. Blood will be drawn at the second screening visit and yearly thereafter on all patients enrolled in the Database. Standardized methods for serum, plasma, DNA, and liver tissue processing that allow for maximal preservation of banked specimens and storage in designated -70 degrees C freezers will be applied across all clinical centers or at the NASH CRN central repository (see NAFLD Database Standard Operating Procedures I: Clinical Center Operations).

NAFLD Database Protocol

7. Statistical and design considerations

This is a clinicopathologic condition-based database designed primarily to allow the compilation of data and collection of specimens for the purpose of the study of the epidemiology and natural history of NAFLD. The study also aims to recruit patients for participation in randomized, controlled therapeutic trials. The recruitment goal is a database of 1500 patients with NAFLD with at least 48 weeks of follow-up.

The primary and secondary objectives of the NAFLD Database, as specified in Sections 2.1 and 2.2 of the protocol, are intentionally very broad. Since this is the largest and most comprehensive study of NAFLD, it is expected that many, as yet unasked, questions related to the etiology, natural history, diagnosis, treatment, and prevention of NAFLD will be answered.

Addressing the questions that arise in connection with the NAFLD Database will require the full gamut of statistical analysis procedures, from survival analysis to ROC curves. Nearly all questions will require identification of appropriate subgroups of patients from all clinical centers contributing to the NAFLD Database with analyses tailored to the hypothesis or question to be addressed.

This process will be accomplished through formal publication proposals submitted by investigators to the NASH CRN Steering Committee. Each of these proposals must include a justification for the sample size and plan for statistical analysis constructed with the help of the Data Coordinating Center. Each proposal must contain the following information:

- Specification of the primary and secondary outcome variables
- Specification of subgroups of special interest when making treatment comparisons (e.g., males vs. females or ethnic/racial subgroups)

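### Section 2.3 lists racial/ethnic risk of developing NAFLD as testable, but the Database enrols only people who already have NAFLD or cryptogenic cirrhosis; NASH can be compared only within NAFLD

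*Protocol*

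**What the plan says.** Protocol Section 2.3 introduces its list of eight hypotheses by saying that the information collected "will enable critical hypotheses pertinent to the etiology, pathogenesis, and natural history of NAFLD to be tested". The seventh is that "The risk for the development of NAFLD and NASH in overweight/obese individuals is greater in Hispanic and Caucasian racial/ethnic groups"; the comparison is with African American and Asian groups. The outcome is the development of disease, and the population is overweight or obese individuals.

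The Design synopsis describes the population as "Patients at least age 2 years with definite or suspected NAFLD or cryptogenic cirrhosis". Section 5.1 makes its criteria jointly mandatory ("In order to be enrolled in the Database, patients must satisfy all of the following"). One of them is "Imaging study suggestive of NAFLD or biopsy materials meeting histologic definition of NAFLD or cryptogenic cirrhosis", with imaging plus clinical findings of cryptogenic cirrhosis as the remaining route. Section 4.3 defines the four entry categories, all of them disease categories.

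Section 4.4 gives the expected composition. On entry without histology it says "Twenty percent of the patients are expected to have suspected NAFLD". For the rest of the cohort it says "15% are expected to have cryptogenic cirrhosis, and 65% are expected to have definite NAFLD". Section 7 describes the target in the same terms: "The recruitment goal is a database of 1500 patients with NAFLD with at least 48 weeks of follow-up".

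The protocol describes no NAFLD-free overweight or obese group, no population sampling frame and no external source of denominators.

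**The concern.** To compare the risk of developing a disease between racial/ethnic groups, one needs the number of people at risk in each group as well as the number of cases. The Database selects on having the disease and so observes only cases.

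The racial/ethnic mix of those cases depends on disease risk, but also on who lives in the catchment, who is referred or self-refers (Sections 4.5 and 6.1), and who has a biopsy. Biopsy matters because Section 4.4 caps entry as suspected NAFLD at 20% of projected enrolment.

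At stake is what the study may claim. A directional racial/ethnic risk statement stands in the protocol as something this cohort can test. A later publication proposal could cite it in support of an analysis that the enrolled patients cannot identify.

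**Working it through.** **Inputs.** Total of 1500 (Design synopsis, Sections 4.4 and 7); composition of 20%, 15% and 65% (Section 4.4); entry rules (Sections 4.3 and 5.1); biopsy rules (Sections 6.4 and 6.6). The protocol gives no racial/ethnic counts, risks or catchment sizes, so those used in steps 2 and 3 are assumed and only illustrate the logic.

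**Step 1: the planned composition.**
- Suspected NAFLD: 1500 × 0.20 = 300
- Cryptogenic cirrhosis: 1500 × 0.15 = 225
- Definite NAFLD: 1500 × 0.65 = 975
- Sum: 300 + 225 + 975 = 1500; remainder: 1500 − 1500 = 0

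The stated shares fill the cohort exactly, leaving no planned place for an overweight or obese person without NAFLD or cryptogenic cirrhosis. Patients with cryptogenic cirrhosis fall below the 5% fat threshold when diagnosed by histology, but Section 4.1 enrols them as a probable advanced form of NAFLD. They are not a sample of people at risk of it.

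**Step 2: development of NAFLD.** Let D be the cases and N the overweight or obese people at risk in groups A and B. Then

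risk ratio = (D_A / N_A) / (D_B / N_B).

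The Database supplies D but not N. Assume 900 enrolled cases in A and 600 in B, and, for simplicity, that every case is enrolled:

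| N_A | N_B | Risk A | Risk B | Risk ratio |
|---|---|---|---|---|
| 3000 | 2000 | 900/3000 = 0.30 | 600/2000 = 0.30 | 1.0 |
| 3000 | 4000 | 0.30 | 600/4000 = 0.15 | 2.0 |
| 6000 | 2000 | 900/6000 = 0.15 | 0.30 | 0.5 |

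Identical enrolled data fit no difference, a doubling or a halving. If the fraction of cases enrolled also differs between groups, a second unobserved factor enters.

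**Step 3: development of NASH.** Among overweight or obese people,

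P(NASH) = P(NAFLD) × P(NASH given NAFLD).

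The Database can inform only the second factor. Assume it is 0.50 in both groups:
- P(NAFLD) 0.30 and 0.30: 0.150 / 0.150 = 1.0
- P(NAFLD) 0.45 and 0.225: 0.225 / 0.1125 = 2.0
- P(NAFLD) 0.225 and 0.45: 0.1125 / 0.225 = 0.5

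The conditional comparison is legitimate in itself, but it does not determine the unconditional risk that the bullet names.

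**Step 4: what remains estimable.** NASH versus simple steatosis needs histology. At entry that means the definite NAFLD group, about 975 patients, and fewer after restriction to the overweight or obese (share not stated). The 300 with suspected NAFLD contribute only if biopsied later. Follow-up histology comes from standard-of-care biopsies (Section 6.6) or biopsies for network trials (Design synopsis); the Database schedules none. Progression from steatosis to NASH is therefore observed only in those selected for repeat biopsy.

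**The case against.** The strongest reply has three parts.

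*The hypothesis names two outcomes.* NAFLD includes simple steatosis, the cohort is meant to span a broad range of severity (Section 2.1), and patients with steatosis are at risk of NASH over 48 to 192 weeks of follow-up. This stands. A reader might infer that the whole hypothesis is untestable, or that 0 of 1500 patients are at risk of anything it names. The documents do not support that: the zero applies to developing NAFLD, while NASH can be compared within NAFLD. What survives is that the within-NAFLD comparison differs from risk in overweight or obese individuals.

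*No analysis is fixed.* Section 7 calls the objectives intentionally broad and requires each publication proposal to bring its own analysis plan, prepared with the Data Coordinating Center. External data are not excluded. It is true that nothing in the protocol proposes to read case shares as risks, and a reader should not infer that it does. But the remark on breadth concerns Sections 2.1 and 2.2, whereas the bullet is specific and directional. None of the models named in Section 7 can create an at-risk denominator from enrolled cases, and no external one is planned.

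*Case mix is not worthless.* Also true. Case counts are the numerator, so it would be too strong to say that they carry no information on risk. They cannot identify the risk ratio without a denominator.

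False positives among suspected cases do not rescue the bullet: they would be misclassified cases, not sampled controls.

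**Conclusion.** The point holds in this limited form. The risk of developing NAFLD by race/ethnicity among overweight or obese people cannot be estimated from Database data alone, and NASH can be compared only conditionally on having NAFLD and liver histology.

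The documented size is that all 1500 planned places go to disease categories and none to a NAFLD-free comparator. This rests on the entry rules and the stated composition. The risk ratios of 0.5 to 2.0 in the working use assumed counts and risks; they show non-identifiability and do not measure bias in this study.

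One of the eight hypotheses is affected. The other seven concern severity, progression or family history within NAFLD and do not share the defect. No sample size, eligibility rule or visit depends on the bullet. The fault lies in what the protocol says the study can conclude, and an analysis plan cannot repair it from enrolled cases.

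**What to change.** Reword the bullet in Section 2.3 along these lines: *among enrolled overweight or obese patients with biopsy-proven NAFLD, the prevalence of NASH (versus simple steatosis) and the severity of fibrosis differ by race/ethnicity.* Add that the comparison is subject to referral and biopsy selection.

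Delete the reference to the risk of developing NAFLD, or name the external population denominator that would supply it. State that incidence and prevalence by race/ethnicity cannot be estimated from the Database alone.

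Leave covariate choice to the analysis proposals, where Section 7 already requires it to be specified. Adjustment for BMI or diabetes is debatable because either may lie on the pathway from race/ethnicity to NASH. Referral source is not a listed data item, so adjustment for it should not be promised.

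The rewording changes one bullet and uses histology, demographics, height and weight already collected under Sections 6.4 and 6.7. It needs no new patients or procedures. The downside is a narrower claim; keeping the broader one would mean obtaining and justifying outside data.

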3.1. NAFLD and NASH

Nonalcoholic fatty liver disease (NAFLD), a term used to encompass the entire spectrum of hepatic fat accumulation disorders, is increasingly prevalent in the United States. Nonalcoholic steatohepatitis (NASH) represents a more severe end of the histopathologic spectrum of NAFLD and is broadly defined by the presence on liver biopsy of lipid-filled liver cells (steatosis) with added necroinflammation (hepatitis) and variable degrees of fibrosis (scarring), in the absence of significant alcohol ingestion.¹⁻⁴ The accumulation of fat, predominantly as triglyceride in the liver cell, is the essential first step in the development of NASH and the defining morphology of all forms of fatty liver disease.⁵ NASH is often associated with hyperlipidemia, particularly hypertriglyceridemia.⁶ Liver biopsy is the diagnostic gold standard and the only means of establishing a firm diagnosis of NAFLD and of determining the grade of fat accumulation, necroinflammation and stage of fibrosis in NASH, the critical factors that reflect disease severity and determine disease progression.⁷ The importance of NASH is emphasized by its increasing prevalence and potential to progress to cirrhosis and end-stage liver disease that may require transplantation or result in disability or death.⁸⁻¹¹

3.2. Epidemiology

Selected autopsy series have found NASH in 3% of lean and up to 19% of obese subjects.¹² NASH is most common in middle-aged persons but is found in all age groups including children.¹³ NAFLD or NASH typically occurs in persons who are overweight or diabetic, but it has recently been shown to occur in subjects with normal body weight and normal glucose tolerance.¹⁴ NAFLD has been found to be the single most common cause of serum aminotransferase abnormalities identified during routine blood testing.¹⁵ NAFLD is increasingly prevalent in the United States.¹⁶⁻¹⁸ Past estimates of the prevalence of NAFLD in the adult U.S. population have ranged from 15-39%, because of varied methods of establishing the diagnosis. These estimates were supported by NHANES III survey data reported in 2001 which indicate the prevalence of NAFLD in the U.S. population to be 7.9%.¹⁶ Studies of the natural history of NAFLD suggest that 10-15% of persons with simple hepatic steatosis (without inflammation and fibrosis) progress to NASH and of those, between 16-30% will have a further progressive course, resulting in fibrosis and cirrhosis.^{11,19} In view of the estimated high prevalence of NAFLD, these figures hold important public health implications even with accepting lower rates of progression to end-stage liver disease. Moreover, these estimates are only likely to increase as the mean body mass of individuals in the U.S. increases.²⁰

3.3. Natural history and progression of NAFLD

The potential of NAFLD to progress to more advanced liver disease, as summarized in Figure 1, is a primary focus of concern.

3.3. Natural history and progression of NAFLD

[figure not shown]

Figure 1: Concepts of the Natural History of NAFLD

With progressive injury, NASH may lose its defining histological feature of steatosis as well as other typical findings such as Mallory bodies, and simply appear as chronic hepatitis or cirrhosis.⁵ This observation, as well as the finding of a significant association of metabolic and lipid abnormalities typical of NASH in patients with cryptogenic cirrhosis, suggests that a substantial proportion of cryptogenic cirrhosis may have evolved from NASH.²¹⁻²³ On the basis of UNOS 1987-1998 data, cryptogenic cirrhosis is the third most common indication for liver transplantation in the U.S. Most studies have been based on relatively small numbers of patients and suffer from selection bias. The natural history of NAFLD and factors associated with its progression are poorly understood. Patients found on initial liver biopsy to have pure steatosis seem to have the best prognosis within the spectrum of NAFLD, whereas features of steatohepatitis or advanced fibrosis are associated with a worse prognosis.²⁴ There is also increasing evidence for a significant risk for the development of hepatocellular carcinoma in patients with cirrhosis arising from NAFLD/NASH.²⁵

